2.3 Safety analysis population

The patients with missing safety data in ITT population will excluded from the safety analysis.

3. Evaluation of baseline characteristics

3.1 presentation of baseline characteristics

Variables of baseline characteristics collected are age (years), gender (male/female), diagnosis (Dyspepsia/PUD), antibiotic resistance pattern, poor adherence, and loss of follow-up. The following table shows the types and presentation of variables.

Variable	Type of variable	Presentation
Age (years)	Continuous	Mean ± standard deviation (range)
Gender (male/female)	Categorical	Number (percentage)
Diagnosis (Dyspepsia/PUD)	Categorical	Number (percentage)
Antibiotic resistance pattern		
Clarithromycin, n (%)	Categorical	Number (percentage)
Metronidazole, n (%)	Categorical	Number (percentage)
Levofloxacin, n (%)	Categorical	Number (percentage)
All-susceptible, n (%)	Categorical	Number (percentage)
Triple-resistant, n (%)	Categorical	Number (percentage)
Poor adherence*	Categorical	Number
Loss of follow-up	Categorical	Number

3.2 Statistical methods for baseline characteristics analyses

Comparisons of baseline characteristics between the tailored therapy and empiric therapy will be performed in the ITT analysis populations. Comparisons between the both groups will be performed using the Pearson's χ^2 , corrected χ^2 or Fisher's exact test for categorical variables and using the Student t test for continuous variables.

4. Evaluation of primary outcomes

4.1 *Helicobacter pylori* eradication rate

Six weeks after completion of therapy, *H. pylori* eradication success is defined as negative result from urea breath test (<4%). If patients would be lost to follow-up urea breath testing, they will be scored as treatment failures in the ITT analysis.

The eradication rate is defined as the number of patients who successful eradicate *H. pylori* divided by the total number of population for analysis. These data are presented with number, percentage, and 95% confidence interval (CI).

4.2 Testing the differences of eradication rates

Testing the differences of eradication rates between the tailored therapy and empiric therapy will be performed using the Pearson's χ^2 , corrected χ^2 or Fisher's exact test in the ITT and PP analysis populations.

4.3 Testing the superiority of the tailored therapy

Testing the superiority of tailored therapy group to empiric therapy group will be performed in the ITT and PP analysis populations using hypothesis testing (one-sided Z test) and derivation of a two-sided 95% confidence interval (CI) of difference based on *H. pylori* eradication rate. If p-value of the testing less than 0.025 and the lower bound of the 95% CI greater than zero, superiority of susceptibility-based therapy over empirical therapy could be concluded.

5. Evaluation of secondary outcomes

5.1 Rate of adverse events

During the 14-day treatment period, the subjects will keep a diary to score any possible side effects or discomforts. The subjects will be asked to grade the severity of adverse events according to their influence on daily activities, experienced as "mild" (transient

and well tolerated), “moderate” (causing discomfort and partially interfering with daily activities), or “severe” (causing considerable interference with daily activities). The side effect score recorded is based on the most severe event. Rate of adverse events is defined as the number of patients with any adverse event divided by the total number of population for analysis. These data are presented with number, percentage.

Comparisons of presence of each adverse event and any adverse event between the tailored therapy and empiric therapy will be performed in the safety analysis populations using the Pearson’s χ^2 , corrected χ^2 or Fisher’s exact test.

5.2 Compliance rate

Compliance was defined as either poor when they had taken less than 80% of the total medication or good when they had taken more than 80% medication. Compliance rate is defined as the number of patients with good compliance divided by the total number of population for analysis. These data are presented with number, percentage.

Comparisons of presence of each adverse event and any adverse event between the tailored therapy and empiric therapy will be performed in the ITT analysis populations using the Pearson’s χ^2 , corrected χ^2 or Fisher’s exact test.

5.3 Other Pre-specified Outcome Measures:

(1) Medical cost per patient of tailored or empiric therapy

Medical cost of one patient is overall cost including visit, endoscopy, H. pylori culture, susceptibility testing, eradication treatment, and adverse event treatment.

Comparisons of medical cost between the tailored therapy and empiric therapy will be performed in the PP analysis populations using Student t test.

(2) Ratio of medical cost to H. pylori eradication rate of each therapy

Ratio of medical cost to H. pylori eradication rate of each therapy is defined as average medical cost of the therapy divided by H. pylori eradication rate of one therapy.

(3) Ratio of incremental medical cost to incremental H. pylori eradication rate of tailored compared with empiric therapy

If one therapy cost less and achieved higher eradication rate than the other one, it will be referred to as dominant strategy. If one therapy yielded higher eradication rate but also cost more, an incremental cost-effectiveness ratio (ICER) will be calculated. Obviously, the tailored therapy will cost more because of additional bacterial culture and antibiotic susceptibility testing. So, if eradication rate of the tailored therapy was higher, the ICER of the tailored therapy will be calculated as the ratio of incremental medical cost to incremental H. pylori eradication rate of tailored compared with empiric therapy (in terms of RMB per incremental eradication percentage). If eradication rate of the tailored therapy was equal to or lower than the empiric therapy, the tailored therapy will not be more cost-effective option and the economic evaluation will not be conducted.

6. Additional analyses

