5.3 Drop out standard

Subjects who sign the informed consent and do not complete the prescribed observation period regardless of when and where to exit, are called drop out.

- (1) Patients found in the study course who do not meet the inclusion criteria or do follow the exclusion standards.
- (2) Patients who get other irrelevant diseases that could affect the assessment on the efficiency and safety of the drug during the test.
- (3) Patients who receive any drug that influences the assessment on the drug.
- (4) Patients who do not strictly take standard medication because of any reason (e.g. severe side effects).

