6.2 Intervention

(1) Empirical therapy

Esomeprazole 20 mg, bismuth potassium citrate 600 mg taken twice a day, amoxicillin 1 g, and metronidazole 500 mg taken three times a day for 14 days.

(2) Tailored therapy

Tailored therapy is based on antimicrobial susceptibility of clarithromycin, metronidazole and levofloxacin. a) If the H. pylori strain of one patient was sensitive to clarithromycin, clarithromycin triple therapy (EAC) will be given: esomeprazole 20 mg, amoxicillin 1 g, and clarithromycin 500 mg taken twice a day; b) If the strain was resistant to clarithromycin but sensitive to metronidazole, metronidazole triple therapy (EAM) will be given: esomeprazole 20 mg, amoxicillin 1 g, and metronidazole 500 mg taken twice a day. c) If the strain was resistant to both clarithromycin and metronidazole but sensitive to levofloxacin, levofloxacin triple therapy (EAL) will be given: esomeprazole 20 mg, amoxicillin 1 g taken twice a day, and levofloxacin 500 mg taken once a day. d) If the strain was resistant to all three antibiotics, bismuth quadruple therapy (EBA₂M₄) will be given: esomeprazole 20 mg, bismuth potassium citrate 600 mg, amoxicillin 1 g taken twice a day, and metronidazole 500 mg taken four times a day. Study treatment regimens will be all given 14 days.

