6.3 Drugs

Esomeprazole, 20mg/tablet, AstraZeneca AB, Sodertalje, Sweden.

Bismuth potassium citrate, 300mg/capsule (110mg elemental bismuth), Dawnrays Pharmaceutical Limited, Suzhou, Jiangsu, China.

Amoxicillin, 250mg/capsule, Ruiyang Pharmaceutical Co. Ltd., Shandong, China.

Clarithromycin, 250mg/tablet, Shanghai Abbott Laboratories Co. Ltd., Shanghai, China.

Metronidazole, 200mg/tablet, Shanghai Xinyi Wanxiang Pharmaceutical Industry Company Limited, Shanghai, China.

Levofloxacin, 500mg/tablet, Daiichi Sankyo Pharmaceutical Beijing Co., Ltd., Beijing, China.

7. *H. pylori* Culture and Antibiotic Susceptibility Testing

Tissue samples will be obtained from gastroscopic biopsy. The biopsy specimens will be cultured and maintained on brain heart infusion agar medium (OXOID, Basingstoke, UK) containing 5% defibrinated sheep blood under microaerophilic conditions (85% N₂, 10% CO₂, 5% O₂) at 37°C. All isolates will be stored in brain heart infusion broth (Difco Laboratory, Detroit, MI, USA) supplemented with 30% glycerol at -80°C. Clinical isolates will be also identified as *H. pylori* using positive tests for urease, oxidase, catalase and Gram staining.

Minimal inhibitory concentrations (MIC) of clarithromycin, metronidazole, and levofloxacin will be determined by the two-fold agar dilution method. *H. pylori* is suspended in saline and measured using a spectrophotometer. The bacterial suspensions (10⁸ colony forming units per milliliter) are then plated with an inoculator (Sakuma Seisaku, Tokyo, Japan) onto agar plates containing various concentrations of above antibiotics. After three days of microaerophilic incubation, MIC is defined as the lowest drug concentration that prevented visible growth of bacteria. ATCC43504 is used as the quality control. Clarithromycin >2 µg/mL, metronidazole >8 µg/mL, levofloxacin >2 µg/mL is defined as resistance breakpoints.

8. Safety evaluation

From the beginning of that patients signed the informed consent and are selected for trial to one month after the end of treatment, any adverse medical events, regardless of whether a causal relationship with the study medication, will be judged to be Adverse Event (AE).

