2.2 Per-protocol (PP) analysis population

All individuals who violated the study protocol, such as patients not taking at least 80% of treatment drugs, or with unknown post-treatment H. pylori status will be excluded from the PP analysis.

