Good Adherence (Took at least 80% of drugs)

Subjects without AEs

Subjects with AEs

Total

AE, adverse event.

Summary of Statistical Analysis Plan Changes

Change	Original	Final
1. Sample size estimation	Assuming 95.7% eradication rate of tailored therapy in our trial, 88.8% eradication rate of empirical therapy, a superiority margin of >0 , a power of 80%, an alpha of 0.05 (one-sided), a ratio of 3:1, at least 340 subjects in susceptibility-based therapy and 114 subjects in empirical therapy will be required to show superiority of susceptibility-based therapy over empirical therapy on the basis of H. pylori eradication rate. Taking into consideration of 10% lost to follow-up, at least 500 participants (374 for tailored therapy and 126 for empiric therapy) is expected to be recruited for the study.	Assuming 96.5% eradication rate of tailored therapy in our trial, 88.9% eradication rate of empirical therapy, a superiority margin of >0 , a power of 80%, an alpha of 0.05 (one-sided), a ratio of 3:1, at least 260 subjects in susceptibility-based therapy and 87 subjects in empirical therapy will be required to show superiority of susceptibility-based therapy over empirical therapy on the basis of H. pylori eradication rate. Taking into consideration of 10% lost to follow-up, at least 382 participants (286 for tailored therapy and 96 for empiric therapy) is expected to be recruited for the study
3.1 presentation of	Variables of baseline characteristics collected are age (years), gender (male/female), diagnosis (Dyspepsia/PUD), clarithromycin-taking	Variables of baseline characteristics collected are age (years), gender (male/female), diagnosis (Dyspepsia/PUD), clarithromycin-taking

Summary of SAP changes

baseline characteristics
	
history, 23S rRNA mutation, antibiotic resistance pattern, poor adherence, and loss of follow-up. The following table shows the types and presentation of variables.
	
history, 23S rRNA mutation, antibiotic resistance pattern, poor adherence, and loss of follow-up. The following table shows the types and presentation of variables.

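### The 80% compliance rule pools all drugs on an unstated counting basis, so a levofloxacin-triple patient who takes no levofloxacin still meets the per-protocol threshold

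*Combined protocol and SAP*

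**What the plan says.** Final protocol 9.2 and Final SAP 5.2 define compliance, a secondary outcome, as "poor when they had taken less than 80% of the total medication or good when they had taken more than 80% medication". The percentage refers to the whole regimen. No passage sets a minimum for any single drug, and none states the unit of counting.

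Final SAP 2.2 (and protocol 10.2) removes from PP "All individuals who violated the study protocol, such as patients not taking at least 80% of treatment drugs", together with patients whose post-treatment status is unknown. The adherence line in SAP Table 5 reads "Good Adherence (Took at least 80% of drugs". Protocol 5.3(4) lists among drop-outs "Patients who do not strictly take standard medication because of any reason", but does not tie that item to the PP set.

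The regimens in Final protocol 6.2 have three or four drugs. The empirical arm receives "Esomeprazole 20 mg, bismuth potassium citrate 600 mg taken twice a day, amoxicillin 1 g, and metronidazole 500 mg taken three times a day". In the tailored arm, patients resistant to clarithromycin and metronidazole but susceptible to levofloxacin receive "esomeprazole 20 mg, amoxicillin 1 g taken twice a day, and levofloxacin 500 mg taken once a day".

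**The concern.** The drugs in a regimen contribute very unequal amounts to a pooled total. Amoxicillin dominates any tablet or capsule count, while levofloxacin is one tablet a day. A pooled 80% can therefore be reached without taking the drug that the susceptibility test selected, and whether that happens depends on the regimen.

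The compliance rate is a secondary outcome. SAP 4.3 tests superiority in both ITT and PP and does not rank the two. The cost comparison (SAP 5.3) and the resistance analyses (SAP 6.2 and Table 4) are run in PP. In Table 4, the tailored patients in the R-R-S row are by protocol 6.2 exactly those assigned levofloxacin triple therapy, so that row is the most exposed.

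**Working it through.** The plan gives no compliance figure to reproduce. The check is direct arithmetic.

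**Inputs.** Doses and frequencies come from Final protocol 6.2. Unit strengths come from 6.3: esomeprazole 20 mg, bismuth potassium citrate 300 mg, amoxicillin 250 mg, clarithromycin 250 mg, metronidazole 200 mg, levofloxacin 500 mg.

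**Formula.** Share taken when one drug is wholly omitted and all others are fully taken = 1 − (daily amount of that drug ÷ daily amount of all drugs). Units per day = dose ÷ unit strength × frequency. A metronidazole dose of 500 mg counts as 2.5 tablets.

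**Units per day.**
- Levofloxacin triple (EAL): 2 + 8 + 1 = 11
- Clarithromycin triple (EAC): 2 + 8 + 4 = 14
- Metronidazole triple (EAM): 2 + 8 + 5 = 15
- Tailored quadruple (EBA₂M₄): 2 + 4 + 8 + 10 = 24
- Empirical: 2 + 4 + 12 + 7.5 = 25.5 if amoxicillin is read as three times daily, or 2 + 4 + 8 + 7.5 = 21.5 if twice daily. The sentence in 6.2 can be read either way.

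**Results.**

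| Regimen and omitted drug | Tablets/capsules | Intakes | Milligrams |
|---|---|---|---|
| EAL, no levofloxacin | 10/11 = 90.9% | 4/5 = 80.0% | 2040/2540 = 80.3% |
| EAC, no clarithromycin | 10/14 = 71.4% | 4/6 = 66.7% | 2040/3040 = 67.1% |
| EAM, no metronidazole | 10/15 = 66.7% | 4/6 = 66.7% | 2040/3040 = 67.1% |
| Empirical, no bismuth (amoxicillin three times daily) | 21.5/25.5 = 84.3% | 8/10 = 80.0% | 4540/5740 = 79.1% |
| Empirical, no bismuth (amoxicillin twice daily) | 17.5/21.5 = 81.4% | 7/9 = 77.8% | 3540/4740 = 74.7% |
| EBA₂M₄, no bismuth | 20/24 = 83.3% | 8/10 = 80.0% | 4040/5240 = 77.1% |

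The levofloxacin row is at or above 80% in all three columns. The clarithromycin and metronidazole rows are below 80% in all three. The bismuth rows change with the column.

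**The boundary.** A patient at exactly 80% is neither below nor above it, so SAP 5.2 assigns no class. Table 5 counts that patient as good, SAP 2.2 keeps the patient in PP, and the Table 1 footnote (poor means less than 80%) agrees with both. The case can occur: by intakes, EAL without levofloxacin is exactly 4/5.

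**The case against.** Several stronger readings are tempting, and the documents do not support them.

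- **That an empirical patient who skips all bismuth always counts as compliant.** This holds by tablets and capsules only. By intakes the patient is on the line or below it, and by milligrams the patient fails.
- **That such patients must stay in PP.** SAP 2.2 excludes protocol violators in general and gives the 80% rule only as an example. A patient who took none of an assigned drug could reasonably be called a violator, and 5.3(4) points the same way. That stands. But neither text names single-drug omission as a PP exclusion, and in an open-label trial the decision would be left to case-by-case judgement.
- **That the rule favours one arm.** The unevenness is by regimen. By tablets and capsules, bismuth omission passes in the tailored quadruple regimen (83.3%) as it does in the empirical one.
- **That a large share of the tailored arm is affected.** The Background gives dual clarithromycin and metronidazole resistance of 21–37% and levofloxacin resistance of 20–54%, so susceptibility of 46–80%. Assuming independence, 0.21 × 0.46 = 9.7% to 0.37 × 0.80 = 29.6% of 286 patients, or about 28 to 85, would be assigned EAL. That counts patients assigned the regimen, not patients who omit levofloxacin. The documents give no rate of omission.
- **That the main eradication result is at risk.** ITT includes every randomised patient whatever their compliance.

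The exactly-80% gap is also narrow if units are counted. Over 14 days, 80% of the total is 123.2 (EAL), 156.8 (EAC), 240.8 or 285.6 (empirical) and 268.8 (EBA₂M₄), none reachable in whole or half units. Only EAM can reach it (168 of 210). By intakes it is reachable more widely.

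**Conclusion.** The point holds in a limited form. The compliance rule has no per-drug requirement and no counting basis. On any of three natural bases it lets a levofloxacin-triple patient who took no levofloxacin meet the PP threshold (90.9%, 80.0%, 80.3%), while the same omission in the other triple regimens fails (66.7% to 71.4%). For bismuth, the answer depends on a basis that the plan leaves open. The boundary at exactly 80% is inconsistent between SAP 5.2 and SAP 2.2 and Table 5.

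This rests on the doses in protocol 6.2, complete omission of one drug, and full intake of the rest. The effect on the PP contrast cannot be sized, because the frequency of such omission is not given. What is affected is the secondary compliance outcome and the PP superiority, cost and resistance analyses. ITT eradication is not. The change should be made because it is cheap and removes a misclassification, not because a bias has been shown.

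**What to change.** In Final protocol 9.2 and 10.2 and Final SAP 2.2 and 5.2:

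- Define good compliance as at least 80% of the prescribed doses of each assigned drug, and poor compliance as below 80% of any one of them. This also settles the counting basis.
- Apply this one definition to the PP set, Tables 1 and 5, and SAP 6.3 and 6.4, with the at-least-80% boundary throughout.
- Make sure the patient diary records intake drug by drug. The protocol provides for a diary, but the form is not in the documents, so it may already do so.

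Under this rule, a patient with no levofloxacin or no bismuth has 0% of that drug, is a poor complier and is outside PP on any basis. The cost is some wording, possibly a diary line per drug, a slightly lower compliance rate and a slightly smaller PP set.

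Separately, the sponsor must reconcile the amoxicillin frequency in the empirical regimen of protocol 6.2, since the prescribed number of doses is the denominator of any compliance rate.

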
Exclusion Criteria
	
 1. Previous H. pylori eradication therapy 2. Less than 18 years old 3. With history of H. pylori infection treatment 4. With previous gastric surgery 5. Major systemic diseases 6. Pregnancy or lactation 7. Allergy to any of the study drugs 8. Administration of antibiotics, bismuth, antisecretory drugs in 8 weeks prior to inclusion

Arms and Interventions
	
1. Empirical therapy
 
Esomeprazole 20 mg, bismuth potassium citrate 600 mg taken twice a day, amoxicillin 1 g, and metronidazole 500 mg taken three times a day for 14 days.
 
2. Tailored therapy
 
Tailored therapy is based on antimicrobial susceptibility of clarithromycin, metronidazole and levofloxacin. according to antibiotic resistance pattern included esomeprazole 20mg bid, amoxicillin 1g bid, with a third drug (clarithromycin 500mg bid, metronidazole 400mg bid, or levofloxacin 500mg qd) for susceptible strains, or with bismuth 220mg bid plus metronidazole 400mg qid for triple-resistant strains. Study treatment regimens were all given 14 days.

Schedule
	
1. Enrollment
 
Obtain written informed form

	
Check eligibility criteria
 
Collect baseline characteristics
 
Undergo upper endoscopy with gastric biopsy and rapid urease testing
 
Conduct bacterial culture and antibiotic susceptibility testing
 
2. Allocation
 
After the written informed consents would be obtained from eligible patients, the independent research assistant will open envelopes by randomization sequence and telephone study staff to give them each patient's treatment allocation. Eligible patients will be randomly allocated to receive either tailored therapy or empirical therapy in a 3:1 ratio.
 
3. treatment
 
Study treatment regimens were all given 14 days. During the treatment period, the subjects kept a diary to monitor compliance and symptoms.
 
4. Follow-up
 
After the end of treatment, adverse events and compliance was surveyed. Six weeks after completion of therapy, H. pylori eradication was assessed by ¹³C-urea breath testing.

Outcome Measures
	
Primary Outcome Measure:
 
1. Helicobacter pylori eradication rate
 
Six weeks after completion of therapy, H. pylori eradication success is defined as negative result from urea breath test (<4%)
 
Secondary Outcome Measure

Final Protocol

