Now culture-based susceptibility testing for *H. pylori* is rarely performed in standard practice. This may be due to several major limitations: they are time-consuming, costly, and invasive procedures, culture difficulty, and et al. So empirical therapy would be needed for most patients over the world. In the settings with high antibiotic resistance, only bismuth quadruple therapy (BQT) is the recommended first-line treatment, and any non-BQT therapy (triple, concomitant, hybrid, or sequential) would not be more effective option.(1) Our previous study showed that substitution of amoxicillin for tetracycline in a 14-day BQT containing 1,600mg/d of metronidazole eradicated 96.4%(54/56) of metronidazole susceptible strains and 93.3%(42/45) of metronidazole resistant strains when used as first-line *H. pylori* therapy.(10). Fewer studies had

compared the effect of susceptibility-based therapy versus BQT for first-line *H. pylori* eradication, except one.(11)

In this study, we will evaluate the efficacy, safety and compliance of pretreatment culture and susceptibility-based tailored therapy to treat naïve patients with *H. pylori* infection. Susceptibility-based therapy will use [name] DY et al's recommendation, in which proton pump inhibitors, amoxicillin, and third susceptible drug triple therapies will be given after testing the susceptibility to clarithromycin, metronidazole and levofloxacin, or bismuth quadruple therapy was given if no susceptible antibiotics.(12) The comparator is novel bismuth quadruple therapy in which tetracycline was replaced by amoxicillin, without reference to antimicrobial susceptibility.

2. Objective

[figure not shown]

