5.1 Inclusion criteria

- (1) Participants with non-ulcer functional dyspepsia or scarred peptic ulcer disease;
- (2) Ability and willingness to participate in the study and to sign and give informed consent;
- (3) confirmed H. pylori infection with positive results on both rapid urease testing and culture

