6.2 Effect of antibiotic resistance on eradication rate

Comparisons of eradication rate of one therapy between antibiotic susceptible and

resistant strains will be performed in the PP analysis populations using the Pearson's χ^2 , corrected χ^2 or Fisher's exact test.

Additional comparisons of eradication rate of antibiotic resistant strains between the tailored therapy and the empiric therapy will be performed in the PP analysis populations using the Pearson's χ^2 , corrected χ^2 or Fisher's exact test.

6.3 Effect of presence of adverse events on compliance.

Comparisons of compliance rate of one therapy between presence and absence of adverse event will be performed in the safety analysis populations using the Pearson's χ^2 , corrected χ^2 or Fisher's exact test.

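### The cost definition counts culture and susceptibility testing in both arms, while the cost-effectiveness section treats testing as an extra cost of tailored therapy only; no rule says which arm is charged

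*Combined protocol and SAP*

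**What the plan says.** Cost-effectiveness is secondary objective (3) of the Final Protocol (2.2). The cost measures are listed in 9.3, among the other pre-specified outcomes.

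- **Cost definition.** Final Protocol 9.3(1) and Final SAP 5.3(1) use the same sentence: "Medical cost of one patient is overall cost including visit, endoscopy, H. pylori culture, susceptibility testing, eradication treatment, and adverse event treatment". It covers tailored and empirical patients alike, with no arm-specific rule. The SAP compares cost between arms with a t-test in the per-protocol population.
- **Cost per eradication.** SAP 5.3(2) divides each therapy's average cost by its eradication rate.
- **ICER.** SAP 5.3(3) states: "Obviously, the tailored therapy will cost more because of additional bacterial culture and antibiotic susceptibility testing". If tailored therapy eradicates more, "the ICER of the tailored therapy will be calculated as the ratio of incremental medical cost to incremental H. pylori eradication rate". If it eradicates no more than the comparator, no economic evaluation is done. The same paragraph also has a dominance rule: "If one therapy cost less and achieved higher eradication rate than the other one, it will be referred to as dominant strategy".
- **Who is tested.** Eligibility requires "confirmed H. pylori infection with positive results on both rapid urease testing and culture" (Final Protocol 5.1). The Final Protocol abstract lists "Conduct bacterial culture and antibiotic susceptibility testing" under Enrollment, and the schedule puts this at day -14, ahead of allocation at day 0.
- **Who uses the result.** The comparator is given "without reference to antimicrobial susceptibility" (Final Protocol, Background).

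**The concern.** Two statements in the same SAP section cannot both describe the calculation. Under 5.3(1) an empirical patient's cost includes the culture and susceptibility tests that patient had at entry. Under 5.3(3) those tests are what make the tailored arm dearer. An analyst who follows 5.3(1) drops testing from the difference between arms; one who follows 5.3(3) keeps it. Both can claim to have followed the plan.

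The price of testing is central to the economic case for tailoring, and the Final Protocol Background itself names cost as one reason culture-based testing is rarely done. A calculation that charges the empirical strategy for tests it does not use would favour tailored therapy.

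**Working it through.** The documents state no cost, unit price or ICER, so there is no figure of the plan to reproduce. The check is a comparison of passages followed by algebra.

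**Step 1: are empirical patients tested?** Yes. Positive culture is an entry criterion, susceptibility testing is an enrolment procedure without distinction by arm, and Final SAP 6.2 plans "Additional comparisons of eradication rate of antibiotic resistant strains between the tailored therapy and the empiric therapy", which needs results in both arms.

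**Step 2: notation.** T is the cost of culture plus susceptibility testing per patient. D is the difference in all other cost, tailored minus empirical (mainly drugs and adverse-event care). The planned gain is 96.5 − 88.9 = 7.6 percentage points (Final SAP section 1).

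**Step 3: the two readings of the ICER.**

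- Testing in both arms (5.3(1) taken literally): incremental cost = (T + D) − T = D, so ICER = D/7.6.
- Testing in the tailored arm only (the premise of 5.3(3)): incremental cost = T + D, so ICER = (T + D)/7.6.
- Gap between readings: T/7.6, whatever D is.

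With T assumed, in RMB, and results in RMB per percentage point:

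| T | D | Both arms | Tailored only | Gap |
|---|---|---|---|---|
| 100 | 0 | 0.0 | 13.2 | 13.2 |
| 300 | 0 | 0.0 | 39.5 | 39.5 |
| 500 | 0 | 0.0 | 65.8 | 65.8 |
| 1000 | 0 | 0.0 | 131.6 | 131.6 |
| 500 | −200 | −26.3 | 39.5 | 65.8 |
| 500 | 200 | 26.3 | 92.1 | 65.8 |

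**Step 4: when the conclusion changes.** If tailored therapy eradicates more and D lies between −T and 0, the literal reading gives a negative incremental cost, so tailored therapy is dominant under the SAP's rule. The other reading gives a positive incremental cost and an ICER. The row with T = 500 and D = −200 is an example.

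**Step 5: the other two measures.** Under the literal reading the t-test in 5.3(1) compares D alone. The empirical ratio in 5.3(2) is raised by T/0.889: 100/0.889 = 112 RMB per eradication at T = 100, and 500/0.889 = 562 at T = 500.

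**Step 6: the decision rules.** 5.3(3) takes it as settled that tailored therapy costs more, then decides from eradication alone whether to compute an ICER or to stop. If computed costs came out lower for the tailored arm, computing an ICER whenever it eradicates more would conflict with the dominance rule. Stopping when it eradicates less would skip a cheaper but less effective trade-off.

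**The case against.** The best defence is that 5.3(3) shows the intent. It is the plan's only statement on how testing enters the incremental comparison, and there testing does not cancel. On this view the list in 5.3(1) names components to be counted, and 5.3(3) shows which arm bears testing. This stands as evidence of intent, but it does not close the gap. The sentence predicts a result; it does not lay down a costing rule. Final Protocol 9.3 carries the definition without it, and the measures in 5.3(1) and 5.3(2) rest on the definition alone.

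Three stronger readings are tempting and are not supported:

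- **That the cost-effectiveness objective cannot be answered.** An attribution rule answers it, without redesign. Even under the literal reading an ICER can be computed; it would omit testing.
- **That the plan is biased towards tailored therapy.** The bias arises only if 5.3(1) is applied literally and 5.3(3) is disregarded.
- **That the tailored drugs are cheaper, so D is negative.** Taking Final Protocol 6.2 doses over 6.3 strengths at face value, the tailored triple regimens need 11 to 15 tablets or capsules a day, against 21.5 or 25.5 for the empirical regimen, depending on how the amoxicillin frequency is read. Counts of different drugs are not prices, and the tailored quadruple regimen needs 2 + 4 + 8 + 10 = 24. The sign of D is unknown.

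A reader might also want biopsy endoscopy removed from the empirical arm. That is a preference: both arms enter through endoscopy with rapid urease testing, and nothing in the documents conflicts on it.

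**Conclusion.** The concern holds as an inconsistency between Final SAP 5.3(1) (with Final Protocol 9.3) and Final SAP 5.3(3), with no attribution rule to settle it. It is more than missing detail, because the stated definition, followed as written, leaves the test that defines the tailored strategy out of its incremental cost.

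The size is T/7.6 on the ICER, about 13 RMB per percentage point for each 100 RMB of T, plus T/0.889 on the empirical arm's cost per eradication. This assumes the planned eradication rates and a testing price common to both arms. All RMB values are illustrations. Whether the economic conclusion would reverse depends on D, which the documents do not allow one to estimate. The point should be corrected before the economic analysis; it does not touch the primary or safety analyses.

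**What to change.** 1. In Final Protocol 9.3(1) and Final SAP 5.3(1), state that culture and susceptibility testing are charged to the tailored arm only, and that trial-mandated testing in the empirical arm is excluded as research cost.
2. Use these totals in the t-test, the cost per eradication and the ICER.
3. In SAP 5.3(3), replace the premise that tailored therapy must cost more with this rule. Let the computed costs and eradication rates decide dominance and whether the economic evaluation is done.

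The cost is wording and a small change to the analysis. It needs testing cost to be separable from other costs; the definition lists the components separately, but the documents do not confirm that they are recorded item by item. The downside is a less favourable economic result for the tailored arm than under the literal reading.
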